These analyses showed that offering routine HIV testing and counseling with moderate and high-risk populations also would be cost effective in terms of quality-adjusted life-years gained¹ (Paltiel et al., 2005; Sanders et al., 2005). The CDC recommends the routine use of screening for populations with HIV prevalence rates that are 1% or greater. In these populations, Sanders et al. (2005) estimate the incremental cost-effectiveness ratio of one-time screening to be \$41,736 per quality-adjusted life-year. This figure considers only the benefit to the identified patient (not the possible benefit to sexual partners as a result of potential decreased HIV transmission risk) and is based on a one-time screening program increasing life expectancy by 3.92 days, or 2.92 quality-adjusted days, at a cost of \$333 relative to current practice. Paltiel et al. (2005) estimate the incremental cost-effectiveness ratio of one-time screening to be \$38,000 per quality-adjusted life-year gained; notably, both of these estimates are less than the usual threshold for cost-effective care, which is \$50,000 per quality-adjusted life year gained. Screening is even more cost-effective for high-risk populations (HIV prevalence > 3.0%). The effect of reducing the annual rate of HIV transmission (see discussion below) dramatically increases the cost-effectiveness of screening. Sanders et al. (2005) estimated that one-time screening in a population with a 1% prevalence of HIV infection would reduce the annual rate of transmission by 20%. When taking into account the costs and benefits of one-time screening to sexual partners, the cost of screening would be reduced from an incremental cost effectiveness ratio of \$41,736 to \$15,078 per quality-adjusted life year gained.

Reason #2: Knowledge of one's serostatus and risk reduction counseling reduces sexual risk behaviors

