4.0 STUDY AIMS AND HYPOTHESES

Primary Outcome

The primary outcome is composite STI incidence at 6-month follow-up in which a person is considered positive for STIs if they are positive on any tested STI.

Secondary Outcomes

Secondary outcomes include self-reported sexual risk behavior, being under the influence of substance and/or illicit drug use during sexual activity and cost and cost-effectiveness. The sexual risk and substance use behavior secondary outcomes will be measured at baseline and six months post-randomization as the self-reported number of unprotected sex acts (vaginal and/or anal sex without a condom) and sex while high on drugs or alcohol, which will be measured as the number of sexual occasions when substance use was involved. The cost analysis will consider the budgetary perspective of STD clinics, because decision makers in these programs may be unwilling to implement HIV counseling and testing unless they are reimbursed for costs according to their clinic's budgetary guidelines. The cost-effectiveness analysis will be conducted from the societal perspective (Hall et al., 2008), taking into account the time and expenses incurred by participants. Cost-effectiveness from payer perspectives will be considered in secondary analyses.

4.1 **Primary Aim and Hypothesis**

Aim 1: To determine the effectiveness of brief, participant-tailored prevention counseling in reducing STI incidence among patients seeking medical or health services at STD clinics

H1: The incidence of STIs among participants offered an HIV test with counseling will differ from participants offered an HIV test with information only.

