
wage rates) or client volume (e.g., overhead).

Cost-Effectiveness: We will evaluate the cost-effectiveness of counseling and testing compared to information only and testing, by comparing the additional costs incurred in the counseling arm as described above with potential cost savings from the following sources: (1) avoided costs of treating STIs, (2) avoided costs incurred for individuals with untreated or ineffectively treated STIs, (3) avoidance of increased HIV transmission susceptibility with an STI and (4) lower HIV incidence due to risk behavior change. Table 2 summarizes this approach with representative data. STI treatment costs will be determined from the clinics and compared to published estimates, costs of complications of untreated STIs will be derived from the literature on the cost-effectiveness of STI screening, and data on HIV transmission risks will be from meta-analyses. We will use the results from the trial primary outcome to determine the impact of the counseling arm on reducing new STIs of each type, and multiply each of the STIs avoided by the weighted average cost of treated and untreated STIs (depending on the proportion likely to be treated in a non-research setting). This will provide us with an estimate of direct cost savings from the intervention. We will then consider the additional cost savings from avoiding HIV transmissions across a range of HIV incidence estimates, to determine the "threshold" incidence at which the intervention will be cost-saving. Secondary cases of STIs or HIV avoided among partners of the participants will not be considered in the primary analysis, but their impact can be estimated in a similar threshold analysis.

TABLE 2: STD Treatment Costs					
STD	Cost to treat (F=female, M=Male)	Long-term complications if untreated	HIV susceptibility multiplier		
Neisseria gonorrhea	\$37 (F), \$40 (M)	pelvic inflammatory disease, ectopic pregnancy, infertility, urethritis, epidymytis	2.1		
Chlamydia trachomatis	\$42 (F), \$45 (M)				
Syphilis	\$53	advanced disease**	2.2		
HSV-2	\$800 (F), \$450 (M)	relapse, maternal-fetal transmission	2.5		
Trichomonas vaginalis	\$46	preterm delivery	2.7		
HIV	\$303,100	advanced disease**	1.5		
*discounted lifetime cost from time of infection (Schackman et al. 2006) **maternal-fetal transmission is rare in the United States due to effective prenatal					
screening					

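### Section 10.4.2 defines the cost-effectiveness outcome as a net-cost comparison, so if counseling works at a positive net cost the analysis cannot say whether it is cost-effective

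*Protocol*

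**What the plan says.** Section 4.0 of the protocol lists cost and cost-effectiveness among the secondary outcomes and states: "The cost-effectiveness analysis will be conducted from the societal perspective". Section 10.4 repeats this.

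Section 10.4.2 gives the method. Cost-effectiveness is to be evaluated "by comparing the additional costs incurred in the counseling arm as described above with potential cost savings from the following sources", followed by four sources: treatment of STIs, the consequences of untreated or poorly treated STIs, the raised susceptibility to HIV that an STI brings, and lower HIV incidence through behavior change. The primary outcome is used to "determine the impact of the counseling arm on reducing new STIs of each type". The next step is to "multiply each of the STIs avoided by the weighted average cost of treated and untreated STIs", and of this product the protocol says: "This will provide us with an estimate of direct cost savings from the intervention". HIV transmissions avoided are then added as further savings over a range of HIV incidence, to find the "incidence at which the intervention will be cost-saving".

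Section 3.1, in reviewing published models of HIV screening, quotes $41,736 and $38,000 per quality-adjusted life-year (QALY) and comments: "notably, both of these estimates are less than the usual threshold for cost-effective care", giving that threshold as $50,000 per QALY.

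**The concern.** The named outcome and the stated method answer different questions. A cost-effectiveness analysis sets a cost difference against a health effect. The comparison in 10.4.2 sets dollars against dollars, which makes it a net-cost (cost-offset) analysis with a break-even point.

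The protocol's background keeps the two ideas apart. The screening programs in section 3.1 have a positive cost per QALY, so they do not save money, yet they are called cost-effective. Under the 10.4.2 method, counseling with the same profile would be described only as falling short of cost-saving.

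The secondary outcome is meant to inform policy on whether counseling should accompany rapid HIV testing. An effective intervention with a modest net cost is a plausible result of this trial, and it is the one for which 10.4.2 plans no value-for-money statement.

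**Working it through.** The protocol states no cost-effectiveness result, so there is no figure to reproduce. The check is a comparison of the sections, followed by an illustration.

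**Comparison of what is promised and what is planned**

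| Element of a cost-effectiveness result | Where it stands |
|---|---|
| Incremental cost | Planned: cost per participant by arm, 10.4.2 |
| Health effect | Estimated as a step (STIs avoided by type, 10.4.2), then multiplied by a cost per STI |
| Ratio of the two | Not planned |
| Value against which a ratio is judged | Not given for this trial; $50,000 per QALY appears only as background in 3.1 |
| Result stated instead | HIV incidence at which counseling is cost-saving |

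**Inputs for the illustration**

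- Risk difference RD = 0.032, from the 3.2-point design difference in section 10.6.
- Cost of one HIV infection = $303,100, from Table 2.
- Cost saved per STI, S: Table 2 lists treatment costs from $37 to $800. I assume $40 to $800. Complications of untreated STIs, which 10.4.2 also counts, are not priced in Table 2 and would raise S.
- Added cost of counseling per participant, C: not in the protocol. I assume $20 to $100.

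**Formulas**

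- Net cost per participant = C − RD × S
- Net cost per participant with an STI averted = (C − RD × S) / RD
- Break-even HIV infections avoided per participant = (C − RD × S) / 303,100

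RD is a difference in the proportion of people with any STI. The illustration therefore prices each such person as one infection at cost S.

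**Results**

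*Middle case, C = $50 and S = $40.* The STI saving is 0.032 × 40 = $1.28. Net cost is 50 − 1.28 = $48.72. The ratio is 48.72 / 0.032 = $1,522.50 per participant with an STI averted. Break-even is 48.72 / 303,100 = 0.000161, about 16 HIV infections avoided per 100,000 participants.

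*High net cost, C = $100 and S = $40.* Net cost is 100 − 1.28 = $98.72. The ratio is 98.72 / 0.032 = $3,085. Break-even is 98.72 / 303,100, about 33 per 100,000.

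*Low net cost, C = $20 and S = $800.* The STI saving is 0.032 × 800 = $25.60. Net cost is 20 − 25.60 = −$5.60. Counseling reduces STIs and saves money, so it is dominant and no ratio is needed.

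In the first two cases 10.4.2 as written yields only the break-even figure, which it would restate as an HIV incidence. That restatement needs an assumed relative reduction in HIV. The ratio needs only the incremental cost, the cost per STI and the STI effect, all of which the protocol already plans to obtain.

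**The case against.** The strongest reply is that both parts of a ratio are already planned and only the division is unstated, which an analysis plan could supply. The first half is right: it would be wrong to say that no health effect is measured, because STIs avoided by type are estimated. The second half is weaker. The protocol does not leave the method open; it says how cost-effectiveness will be evaluated and what the end result will be. An analysis plan that followed it faithfully would carry the mismatch forward.

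Four stronger readings are tempting, and the document does not support them.

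- A reader might infer that the analysis is built to come out against counseling. Section 10.4.2 states no decision rule. It reports a threshold over a range of HIV incidence, the STI effect is reported separately as the primary outcome, and net savings with fewer STIs would be a favorable result.
- A reader might infer that leaving out partners contradicts the societal perspective. The protocol says openly that "Secondary cases of STIs or HIV avoided among partners of the participants will not be considered in the primary analysis", and the same sentence allows their impact to be estimated in a similar threshold analysis. A participants-only base case with an extension is a legitimate choice. The fall from $41,736 to $15,078 per QALY in section 3.1 when partners are counted concerns one-time HIV screening. Here both arms receive the HIV test and the contrast is counseling, so that change cannot be carried over.
- A reader might take $50,000 per QALY as this trial's own criterion. It appears only in the review of published screening models and is not adopted for this analysis.
- A reader might want to know how much lower the required HIV effect would be under a QALY criterion. That depends on the QALYs lost per HIV infection, which the protocol does not give.

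**Conclusion.** The point holds in a limited form. The method fixed in 10.4.2 is a net-cost analysis and does not deliver the cost-effectiveness result that sections 4.0 and 10.4 name. The gap matters when counseling reduces STIs at a positive net cost, and is harmless when it reduces STIs and saves money.

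Under the assumed inputs, net cost runs from −$5.60 to +$98.72 per participant at the design effect. The positive cases worked above correspond to about $1,522 and $3,085 per participant with an STI averted, and neither figure is planned for reporting. These amounts show the kind of result that would be missing. They are not forecasts, since C is assumed and S is taken over roughly the range of Table 2 treatment costs.

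This concerns a secondary outcome. The primary comparison of STI incidence is unaffected. The change is worth making because it is cheap and lets the trial answer a question it sets itself.

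**What to change.** In section 10.4.2, make an incremental cost-effectiveness ratio the cost-effectiveness result. At minimum this is net cost per STI averted or per participant with an STI averted. State which, since the composite primary outcome counts people while the savings step counts infections by type. Give uncertainty by bootstrapping cost and outcome jointly; 10.4.2 already names a non-parametric bootstrap for mean costs. Because a ratio is unstable when the STI difference is near zero, show the joint distribution of cost and effect alongside it. Keep the cost-saving HIV-incidence threshold as an additional result.

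A cost per QALY, with literature inputs and sensitivity ranges, is an optional extension. Its drawback is reliance on external values.

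If the sponsor prefers the present method, rename the outcome a net-cost (cost-offset) analysis in sections 4.0, 10.4 and 10.4.2 and wherever else cost-effectiveness is promised.

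The cost is a few sentences of protocol text and some extra analysis, with no new trial data.

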10.5 Overview of Analysis Plan

The primary outcome will be analyzed using logistic regression for the binary outcome, new diagnoses of STIs (Yes/No). The logistic regression analysis will predict 6-month STI incidence as a function of randomization group controlling for the baseline incidence of STI. The test of the

hypothesis will be based on a likelihood ratio test comparing the model with and without the indicator for randomization group.

ANCOVA will be used for the secondary continuous outcomes, number of sexual risk behaviors and number of sexual episodes involving substance use. For example, the number of sexual risk behaviors at 6 months will be the outcome and the level of sexual risk behaviors at the baseline assessment will be the only covariate. The STI outcome, the test of the hypothesis will be based on an ANCOVA type specification test comparing models with and without the randomization group indicator. Costs will be compared based on study records supplemented by site-level data collection as described above. All analyses will be performed under intent-to treat (ITT) criteria.

The planned subgroup analyses will test for differences between sets of subgroups (MSM versus non-MSM, African American versus all other race/ethnic groups, men versus women, young (<25) versus older) on the difference in rates of STI by treatment status. Planned exploratory analyses will calculate effect-sizes for subgroups, defined by MSM, heterosexual male, female, all racial/ethnic categories, presence of STI at baseline and use of (any) substances during sex at baseline. Planned exploratory analyses will also examine the extent to which the covariates explain variability in outcomes. First, the baseline levels of condom use self-efficacy, substance use/abuse and depression will be assessed for any potential moderating (interaction) effects on the hypothesized outcomes. Second, the impact of the intervention on these same set of variables will be assessed. For any of these covariates that are affected by the intervention, additional analyses will examine the relationship between changes in these potential mediators and study outcomes. Note that true tests of mediation are not possible due to the lack of temporal precedence in these changes. Prior to all analyses the distributions of outcomes will be examined and the appropriateness of planned analysis strategies assessed. For example, sexual risk and drug use frequently have the characteristics of a count variable. If this is the case, the ANCOVA framework will be utilized within the context of a Poisson, Zero-inflated Poisson or a Negative Binomial model, depending on which has the best fit to the data.

Missing data is a ubiquitous problem in human subject research, primarily due to dropping out and refusal. Missing data can lead to biased estimates and reduction of power, impacting the generalizability of the study. While we will make every effort to minimize the amount of missing data, in follow-up analyses we will attempt to assess the impact of the missing observations. Missingness patterns will be identified and analyses will be conducted to determine if there is a differential attrition by treatment arm, and if missingness is related to any of the covariates. If nonrandom missingness is of concern, this problem can be addressed by applying propensityscore matching so that the impact of bias can be assessed.

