10.2 Randomization

Participants will be randomized to one of two treatment groups. Randomization will be stratified by site and within site, by race/ethnicity, gender and within males, by MSM versus heterosexual. The randomization procedure will be conducted in a centralized process through the Duke Clinical Research Institute (DCRI). Specifically, randomization schedules will be created by the study statistician for each randomization stratum within each site. The race/ethnicity categories will include: African American, Hispanic, European American, and other). Note that Hispanics of African origin will be classified as Hispanic for the purpose of randomization. The randomization schedules will be of a randomized-block nature to ensure relative equality of assignment across condition across the recruitment period and to prevent the potential for study staff quessing the next assignment which is heightened when a fixed block-size is used. After providing Informed Consent and subsequently completing the baseline assessment on ACASI and the STI testing, the site research coordinator (or designee) will perform the randomization. The research coordinator will contact the central randomization center to determine the appropriate condition for the site. The method of this notification will be by computer-assisted telephone. The research coordinator will enter the appropriate participant characteristics (site, participant ID, gender and ethnicity) by pushing appropriate telephone buttons. The treatment assignment will then be transmitted by computer voice (by telephone) and by fax or computer screen. The DCRI statistician will review the randomization data on a regular basis to ensure that the scheme is being implemented according to plan.

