10.6 Statistical Power and Sample Size Calculation

All power calculations assume that the Type I error rate, α , is .05. Power calculations for main effects for treatment were made with PASS 2005. Power for interaction effects was calculated using a simulation program written in SAS 9.1.3. The original RESPECT study showed a significant effect of 6-month rate of new STIs which were 7.2% in the counseling arm and 10.4% in the didactic arm, for a difference of 3.2%. Though underpowered to be definitive, subgroup analysis of RESPECT-2 suggested that there is a differential effect of counseling on MSM compared to heterosexuals.

We therefore decided to power this study both to uncover a risk difference of 3.2% (with a higher base rate of STI incidence of 12.0%) and to have sufficient power to test for an interaction between MSM and non-MSM in which the ratio of risk ratios was approximately 2.0. Simulations showed that to have over 80% power for both the 3.2% risk difference overall and a 2 fold risk ratio interaction between MSM and other study participants required 1663 per group or 3326 total sample at the six month assessment. Although we anticipate closer to 85% follow-up, we used the conservative assumption of 70% retention for calculation of power. With the assumption of 70% retention, this means that 5000 must be randomized. Simulations assumed that 1/3 of the participants were MSM. Power for other, separate sub-group comparisons should be similar to that described above for MSM vs. non-MSM as long as the smaller subgroup in the comparison approaches or exceeds a third of the sample composition, which is consistent with the data we have obtained from the sites. For the secondary hypotheses of sexual risk behavior and substance use during sex there will be over 80% power to uncover a standardized difference between groups of .10, which is considered a small effect.

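### Randomization is stratified by site, race/ethnicity, gender and MSM status, but the stated efficacy models omit these factors: the test stays valid, at a possible small cost in power

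*Protocol*

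**What the plan says.** Protocol Section 10.2: "Randomization will be stratified by site and within site, by race/ethnicity, gender and within males, by MSM versus heterosexual". Section 6.0 says the same. Section 10.2 gives four race/ethnicity categories and Section 5.2 gives 9 clinics.

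Protocol Section 10.5 specifies a logistic model for new STI at 6 months "as a function of randomization group controlling for the baseline incidence of STI", tested by a likelihood ratio test for the arm indicator. The synopsis (Section 2.0) describes the same model. For the secondary continuous outcomes, the worked ANCOVA example states that "the level of sexual risk behaviors at the baseline assessment will be the only covariate".

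The stratification factors appear elsewhere only in other roles: subgroup and exploratory analyses (Section 10.5), variability of effects across sites (Section 5.4.8), and cost modelling by site and participant characteristics (Section 10.4.2). None of them enters a main-effect efficacy model.

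Section 10.2 also lists what is keyed in by telephone to obtain an assignment: "site, participant ID, gender and ethnicity". MSM status is not in that list.

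**The concern.** Stratified randomization removes chance imbalance between arms on the stratifying factors. If those factors also predict the outcome and the model leaves them out, the model-based variance still allows for imbalance that the design has largely prevented. The test then rejects a true null less often than 5% and gives up some power.

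There is reason to expect prognostic strata here. The composite endpoint counts a positive result on any STI tested, and Section 5.4.3 tests different things by group: rectal as well as urine specimens for MSM, trichomonas for women, neither for heterosexual men. The chance of a positive composite therefore depends partly on stratum by construction. Sites were also chosen for diversity (Section 5.3.1).

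The stake is efficiency and agreement between design and analysis, not validity. The telephone list is a separate matter of consistency: schedules exist by MSM status, yet the field that would select among them is not listed.

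**Working it through.** **Inputs.** Section 10.6 states: "All power calculations assume that the Type I error rate, α , is .05". Two-sided testing is assumed, because the hypothesis in Section 4.1 says STI incidence in the counseling arm "will differ from participants offered an HIV test with information only". Section 10.6 also gives a base rate of 12.0% and a difference of 3.2 points (so 8.8%), 1663 per group (3326 in all) at six months, one third MSM, a ratio of risk ratios of about 2.0, and a standardised difference of 0.10 for secondary outcomes. STI rates by stratum and block sizes are not given. Both are assumed below.

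**The plan's own figures first.**
- Main effect: n = [1.96√(2p̄q̄) + 0.842√(p₁q₁ + p₂q₂)]² / (p₁ − p₂)², with p₁ = 0.12, p₂ = 0.088, p̄ = 0.104. This gives 1428 per group for 80% power. At 1663 per group, power is 85.6%.
- Interaction: Wald test on the log ratio of risk ratios, 12% base rate in both subgroups, overall risk ratio 0.088/0.12 = 0.733. With 0.44 in MSM and 0.88 in the rest, power at 1663 is 80.9% (1626 per group needed for 80%). With 1.1 and 0.55, it is 90.8%.
- Secondary outcomes: δ = 0.10/√(2/1663) = 2.884, and power = Φ(2.884 − 1.96) = 82.2%.

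The statement of over 80% power at 1663 per group therefore reproduces.

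**Size of the model.** There are up to 9 × 4 × 3 = 108 strata. As main effects they add 8 + 3 + 2 = 13 parameters. Expected events are 1663 × 0.12 + 1663 × 0.088 ≈ 346.

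**Secondary ANCOVA, analytic.** Let the strata explain a share R² of the residual variance. The true standard error is then √(1 − R²) times the one the planned model reports. Type I error of the planned model is 2[1 − Φ(1.96/√(1 − R²))]. Planned power is Φ((δ − 1.96)/√(1 − R²)), and adjusted power is Φ(δ/√(1 − R²) − 1.96).

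| R² | Type I error, planned | Power, planned → adjusted |
|---|---|---|
| 2% | 4.8% | 82.5% → 83.0% |
| 5% | 4.4% | 82.8% → 84.1% |
| 10% | 3.9% | 83.5% → 86.0% |

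**Primary test, simulated.** 3326 analysed, 12% against 8.8%, blocks of 4 within strata, 12,000 replicates per setting (Monte Carlo error about 0.2 points on type I error). The planned likelihood ratio test is compared with the same test after adding the 13 main effects.

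| Assumed strength of the factors | Type I error, planned → adjusted | Power, planned → adjusted |
|---|---|---|
| Not prognostic | 5.1% → 5.2% | 86.1% → 86.1% |
| Moderate (site SD 0.3 on the logit scale, odds ratios about 1.7) | 5.0% → 5.2% | 86.9% → 87.2% |
| Strong (site SD 0.6, odds ratios 2.5) | 4.2% → 5.2% | 86.9% → 88.3% |
| Very strong (site SD 0.9, odds ratios 4) | 3.4% → 5.2% | 87.7% → 90.6% |

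In the very strong setting the adjusted fit diverged in some replicates, so that row is indicative only. In the strong setting the mean log odds ratio moved from −0.351 to −0.377.

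**With loss to follow-up.** 5000 randomized, random loss to about 3326, 2,500 replicates (Monte Carlo error about 0.4 points on type I error), stratum effects with logit SD 0.35, 0.5 and 0.8. Planned type I error was 4.9%, 4.8% and 3.8%. Power went from 84.2% to 84.8%, from 84.6% to 87.1%, and from 82.6% to 88.3%.

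**The case against.** The case against acting has several parts.

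- **Conservatism is assumed, not shown.** A reader might infer that the actual type I error is below 5%. The protocol does not support that as a flat statement. It gives no rates by stratum, and with moderate effects, or with realistic loss and SDs up to 0.5, the planned test cannot be told apart from 5%. This stands.
- **Intervals.** A reader might infer that adjustment would narrow the confidence interval. For the logistic model it does the opposite: in simulations the mean standard error of the log odds ratio rose from 0.1076 to 0.1096 (SD 0.35) and from 0.1081 to 0.1116 (SD 0.5). The power gain comes from a larger conditional estimate. This stands.
- **Attenuation.** A reader might call the planned odds ratio biased toward the null. It is non-collapsibility: the less conditional odds ratio is a different, valid target, and Section 10.6 powers the trial on an overall risk difference. This stands, and it shapes the fix.
- **No conclusion depends on it.** Power exceeds 80% either way. At the 85% retention aimed for in Section 5.5.2, 2125 per arm gives about 93%. The MSM interaction test is a separate analysis. This stands and limits the severity.
- **Section 10.5 is an overview, and an SAP may add covariates.** This stands in part. The primary-model sentence is not worded as exclusive, and the exclusive wording sits in a secondary-outcome example. Even so, both sentences state a covariate set, and an SAP that added the strata would depart from the protocol as written.
- **Telephone list.** A reader might infer that the MSM schedule could not be selected. Section 10.2 itself says that schedules exist for each stratum and that implementation is reviewed, and Section 6.0 speaks only of entering client data. This supports a drafting inconsistency, not a failed randomization.

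**Conclusion.** The point holds as a minor efficiency matter, with moderate confidence. The protocol stratifies on four factors and states efficacy models that contain none of them. The planned test is valid. If the factors are prognostic, it is somewhat conservative and less powerful. Over assumed weak to very strong effects, type I error runs from about 5% down to about 3.5%, and the power forgone on the primary test from about 0 to 3 points, reaching about 6 (82.6% against 88.3%) only in the most extreme setting with loss. For the secondary outcomes the loss is about 0.5 to 2.5 points, on a planned power of 82.2%.

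These figures rest on assumed stratum effects, assumed blocks and, where loss is modelled, loss at random. If the factors are not prognostic, nothing is lost. The omission of MSM status from the telephone list is an internal inconsistency to be reconciled.

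**What to change.** **Section 10.5 (and the matching synopsis text).** In the primary and secondary models, include site, race/ethnicity (four levels) and sex/orientation group (female, MSM, heterosexual male) as fixed main effects, alongside arm and the baseline value. Keep the likelihood ratio test for arm. Use main effects rather than the full cross-classification, because 108 cells would be sparse. State that the odds ratio is conditional on these factors, and report a standardised (marginal) risk difference next to it, since the sample size rests on a risk difference.

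**Section 10.2.** Add MSM status to the characteristics entered at randomization, so that the list agrees with the stated strata.

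**Cost.** A few sentences of text, 13 extra parameters against roughly 346 expected events, and a more conditional odds ratio, which the marginal risk difference offsets. No change to sample size or data collection is needed.
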